Appendix H: Radiosensitization Study of Regorafenib and SIR-Spheres Microspheres

Interim Report for Sirtex Medical from University of Oxford

Screening of drugs to quantify radiosensitisation in cancer cell lines

Author: Dr [name], 6th August 2013

Description of the Project

This project aims to quantify the radiosensitisation exerted by drugs licensed for the treatment of metastatic colorectal cancer and hepatoma in a preclinical model system.

A cellular viability assay has been developed to screen drugs for the quantification of intrinsic radiosensitisation (RS) in a semi-automated high-throughput format. The assay has been validated against the current gold standard in cells grown in vitro, clonogenic survival assays. The principal benefit of the cellular viability assay over clonogenic survival assays is that the former can be used to study multiple permutations of dose, temporal sequencing and timing of radiotherapy relative to drug treatment, and a variety of drug concentrations, all in a significantly shorter timescale than the use of traditional methodology.

In the project proposed here, the principal investigator will demonstrate:

1. The degree of radiosensitisation affected by physiologically relevant concentrations of drugs licensed for treatment of colorectal cancer and hepatoma in cancer cell lines
2. The optimal temporal sequencing of each drug with radiotherapy
3. The most appropriate drug concentrations in cell lines to achieve optimal radiosensitisation.

CONFIDENTIAL

STUDY DEVICE: SIR-Spheres®

SCRI INNOVATIONS STUDY NUMBER: GI 189

DATE OF ORIGINAL PROTOCOL: 16 December 2013

Date of Amendment #1: 15 April 2014

Version 2.0

Introduction

Colorectal cancer is the second most common cancer in the developed world (NCI 2010). Although approximately half of cases may be treated with surgery alone, for more advanced stage cancers, including metastatic disease, patient outcomes remain poor. Selective internal radiotherapy (SIRT) permits high doses of radiotherapy to be delivered safely to liver metastases from colorectal cancer. Primary liver cancer, hepatocellular carcinoma (HCC), is not responsive to traditional chemotherapy making it difficult to treat when inoperable. Improving radiotherapy treatment for HCC may benefit from the combinations of radiotherapy with radiosensitising drugs. Although various chemotherapeutics may be used as radiosensitisers, it is not currently clear which radiosensitising agents are most appropriate to improve clinical response rates.

In order to address this research deficit, we have developed a high-throughput assay for the identification of radiosensitising drugs to determine the most appropriate drugs to use with radiotherapy for specific cancers. Historically, screening programmes for intrinsic radiosensitisers have assessed anti-proliferative activity of compound libraries *in vitro* in 4-day assays (Lally *et al.* 2010), or have performed RNA interference to look at the effect of gene expression on response to radiotherapy (Higgins *et al.* 2010). Neither method permits high-throughput screening for radiosensitisers in a manner that directly correlates with the gold standard *in vitro*, i.e. clonogenic assays - where the ability of single cells to form colonies after irradiation is directly measured to enable comparison of radiosensitivity of drugs in different cell lines. Although it is the gold standard, clonogenic assays have major problems as the sole technique for assessing radiosensitivity. They suffer from time-consuming methodology (2 weeks for colony growth) and the expense (a large number of plates and large volumes of media and drugs are required to obtain a single survival curve). Moreover, low plating efficiency for some cell lines can also be problematic (e.g. HepG2 hepatoma cells, which are difficult to test with traditional clonogenic survival assays) and in some cases cannot be overcome. To facilitate the identification of radiosensitising drugs, we developed an assay and confirmed that it could be used as a valid surrogate for clonogenic survival *in vitro*. This assay was then extended robotically to screen compound libraries for potential radiosensitising agents.

Regorafenib is an oral multi-kinase inhibitor developed by Bayer which targets angiogenic, stromal and oncogenic receptor tyrosine kinase (RTK). Regorafenib shows antiangiogenic activity due to its dual targeted VEGFR2-TIE2 tyrosine kinase inhibition. We were asked by Sirtex to prioritise the testing of regorafenib in colorectal cancer cell lines with radiotherapy for this interim report.

CONFIDENTIAL

STUDY DEVICE: SIR-Spheres®

SCRI INNOVATIONS STUDY NUMBER: GI 189

DATE OF ORIGINAL PROTOCOL: 16 December 2013

Date of Amendment #1: 15 April 2014

Version 2.0

Methods

Cell culture. Cell lines derived from colorectal adenocarcinoma (DLD1, RKO and HCT116) were cultured in Dulbecco's modified essential medium (DMEM) supplemented with 10% foetal calf serum, 1x non-essential amino acids and 1x Pen/Strep (Gibco). Cells were grown at 37°C in a humidified incubator in 95% air with 5% CO₂ and passaged twice weekly. All experiments utilised exponentially growing cells with cell population doubling times of approximately 24 hours. Cell cultures were renewed after every 15 passages

Metabolic assays. Proliferation assays were used to optimise cell lines to measure the effects of drugs and/ or radiation. Cells were plated in serial dilutions on 96- or 384-well plates and treated with drugs and/ or radiation as appropriate. After 24 hours, media was refreshed and cells allowed to proliferate for 5-6 cell doubling times. As an indicator of cell proliferation after IR, metabolic activity in each well was measured using a coloured dye converted intracellularly into a yellow-fluorescing form. Cell culture media was replaced with DMEM containing 10 µg/ml dye. After 90 minutes, fluorescence was measured using a BMG Polarstar Optima plate reader.

Clonogenic survival assay. Cells were harvested, diluted to 10000 cells/ml and plated at appropriate cell numbers on 2 x 10 cm dishes/ radiation or drug dose. After 5-6 hours for cell attachment, cells were treated with regorafenib for the timescales stated in the figure legends, and irradiated with 0-8 Gy radiation using a 137-Cs source at a dose rate of ~2Gy/ min. Media were refreshed 24 hours after irradiation, and plates were incubated for 10-14 days. Colonies were stained with 0.4% methylene blue in 100% methanol for colony counting, and results were used to generate clonogenic survival curves.

CONFIDENTIAL

STUDY DEVICE: SIR-Spheres®

SCRI INNOVATIONS STUDY NUMBER: GI 189

DATE OF ORIGINAL PROTOCOL: 16 December 2013

Date of Amendment #1: 15 April 2014

Version 2.0

The following permutations of combination treatment were tested by metabolic assay:

Cell line	Regorafenib concentration range	Timing of addition of drug tested
HCT116 (wild-type)	0 – 40 µM	24 hrs, 6 hrs and 1 hour pre -irradiation
HCT116 (wild-type)	0 – 40 µM	24 hrs, 6 hrs and 1 hour post -irradiation
HCT116 (KRAS mutant)	0 – 40 µM	24 hrs pre-irradiation
DLD1 (wild-type)	0 – 40 µM	24 hrs, 6 hrs and 1 hour pre -irradiation
DLD1 (wild-type)	0 – 40 µM	24 hrs, 6 hrs and 1 hour post -irradiation
DLD1 (KRAS mutant)	0 – 40 µM	24 hrs pre-irradiation
RKO (BRAF mutant)	0 – 40 µM	24 hrs pre-irradiation
RKO (BRAF wild-type)	0 – 40 µM	24 hrs pre-irradiation

CONFIDENTIAL

STUDY DEVICE: SIR-Spheres®

SCRI INNOVATIONS STUDY NUMBER: GI 189

DATE OF ORIGINAL PROTOCOL: 16 December 2013

Date of Amendment #1: 15 April 2014

Version 2.0

Results

1. Measuring radiosensitivity

The metabolic assay was optimised to measure radiosensitivity of regorafenib under different sequencing conditions (drug added 24 h before RT, drug added at same time as RT and drug added 24 h after RT). The data obtained for DLD1 and HCT116 colorectal cancer cells are shown in Figures 1 and 2, which are typical of the results for all cell lines tested under all conditions and permutations. There was no dose-dependent radiosensitisation observed.

[figure not shown]

Figure 1

Figure 1. Regorafenib was added 24 h before radiotherapy treatment of DLD1 cells and cell proliferation measured by relative fluorescence obtained with dye on day 7 post-radiotherapy. There was no significant radiosensitisation observed. IC50 values for drug alone (0 Gy), drug + 3 Gy RT and drug + 6 Gy radiation were 3.2, 2.1 and 3.4 μ M respectively (i.e. no significant difference without and with radiation).

CONFIDENTIAL

STUDY DEVICE: SIR-Spheres®

SCRI INNOVATIONS STUDY NUMBER: GI 189

DATE OF ORIGINAL PROTOCOL: 16 December 2013

Date of Amendment #1: 15 April 2014

Version 2.0

[figure not shown]

Figure 2

Figure 2. Regorafenib was added 24 h before radiotherapy treatment of HCT116 cells and cell proliferation measured by relative fluorescence obtained with dye on day 7 post-radiotherapy. There was no significant radiosensitisation observed.

2. Confirmation of results by clonogenic survival

To confirm the lack of radiosensitisation in all 3 colorectal cancer cell lines, clonogenic survival assays were performed as described above. All 3 colorectal cancer cell lines had sufficient plating efficiency for definitive conclusions to be made. Results are shown in Figure 3, confirming that regorafenib does not cause any statistically significant radiosensitisation of colorectal cancer cell lines in this model system.

CONFIDENTIAL

STUDY DEVICE: SIR-Spheres®

SCRI INNOVATIONS STUDY NUMBER: GI 189

DATE OF ORIGINAL PROTOCOL: 16 December 2013

Date of Amendment #1: 15 April 2014

Version 2.0

[figure not shown]

Figure 3

Figure 3. Clonogenic survival assays for 3 colorectal cancer cell lines treated with regorafenib (10 or 20 μ M) plus radiotherapy (6 Gy). Slight radiosensitisation of RKO cells was observed with 20 μ M regorafenib plus radiation, but no statistically significant radiosensitisation was observed to justify further preclinical testing *in vivo*. Results shown are mean values of three separate experiments.

Conclusions

We have applied 2 types of laboratory assay, including the gold standard test (clonogenic survival), to confirm that regorafenib is not an intrinsic radiosensitiser of colorectal cancer cells. This model system allows assessment of intrinsic radiosensitisation, but it should be noted that it cannot assess the antiangiogenic effect on radiosensitisation. Such exploration would require *in vivo* experimentation in an animal model, which is beyond the scope of this study. The rest of the project will test other approved drugs for intrinsic radiosensitisation of colorectal cancer cell lines and hepatoma cell lines and a further report will be issued in October 2013.

CONFIDENTIAL

STUDY DEVICE: SIR-Spheres®

DATE OF ORIGINAL PROTOCOL: 16 December 2013

Date of Amendment #1: 15 April 2014

SCRI INNOVATIONS STUDY NUMBER: GI 189

Version 2.0

References

CONFIDENTIAL

STUDY DEVICE: SIR-Spheres®

SCRI INNOVATIONS STUDY NUMBER: GI 189

DATE OF ORIGINAL PROTOCOL: 16 December 2013

Date of Amendment #1: 15 April 2014

Version 2.0

**Study Drug:**

**SIR-Spheres® Microspheres**

**Protocol Number:**

**GI 189**

**Prepared By:**

**Innovations**

## **Statistical Analysis Plan Checklist for Investigator Initiated Trials**

### **History of Changes**

This document has undergone the following changes:

Version Number	Version Date	Description of Changes
1.0	22MAY2018	Original document

1.1 Objectives	
Primary Objective:	To evaluate the safety of two treatment cohorts combining regorafenib and SIR-Spheres microspheres (SIR-Spheres) radioembolization in patients with refractory metastatic colorectal cancer (mCRC) with liver metastasis.
Secondary Objectives:	To evaluate the overall response rate (ORR), progression-free survival (PFS), and overall survival (OS) of patients with refractory mCRC when treated with combination SIR-Spheres and regorafenib in the two sequencing cohorts.
1.2 Study Design	
Study Type	 Non-Randomized  Randomized (Allocation Ratio:      )
Details	
This is an open-label study comparing the safety of two treatment cohorts in which radioembolization will be administered using the device SIR-Spheres microspheres (90Y resin microspheres) in combination with regorafenib to patients with mCRC with liver metastases. The two treatment cohorts will be evaluated for safety, ORR, PFS, and OS. Twenty-five patients will be treated in each cohort. The first cohort will complete enrollment before the second cohort opens. There will be no randomization or blinding.
 
Blood samples will be collected from all patients prior to the hepatic angiogram and 99mTc MAA lung shunt scan, on Day 8 after SIR-Spheres treatment, and Day 30 (pre-dose) after SIR-Spheres treatment (see Section 5.1). Expressions of cytokines and proteins will be measured to explore potential biomarkers that may correlate with clinical outcome.

1.3.2 Randomization	
Randomization Type:	 Open-Label  Single Blind  Double-Blind
1.4 Timing of Analysis	
Planned Interim Analysis	 Cohort Review / Dose Escalation  Safety Review  Interim Efficacy/Safety Analysis  Independent DMC/DSMB  Annual Report / Investigator Brochure (IB)  Abstract / Scientific Presentation (Oral/Poster)
Final Analysis	6 months after last patient has been recruited into study
1.5 Responsibilities	
Trial Statistician:	Development of SAP and shells Review deliverables presented by statistical programmers
PK Statistician:	N/A
Independent Statistician:	N/A

1.6 Analysis Software	
Main statistical analysis:	SAS Version 9.3 or above
Other analysis software:	None

1.7 Coding	
 Adverse Events  Medical History	 MedDRA:  Version  Most current release and update coding with new major releases  NCI-CTCAE Version
 Concomitant Medication  Prior Therapy  Subsequent/Further Therapy	 WHO-Drug:  Version  Most current release and update coding with new major releases
3 Analysis Population	
Intent-To-Treat (ITT) Population definition:	 All patients who have started treatment in the study  All patients who have been randomized in the study, regardless of whether they have received any treatment or not  All patients who have been randomized and have started treatment in the study  Other definition, specify:
Per Protocol (PP) Population to be used in analysis:	 Yes  No If yes, please specify the criteria for exclusion from the PP population:
Safety (SAF) Population definition	 All patients who have started treatment in the study. Patients will be analyzed according to the actual treatment they have received.  Other definition, specify:
Other Analysis Population definition:	N/A
4 Baseline Value Definitions	
	Last value prior to first date of study drug treatment
5/6 Efficacy	
Response Criteria Used:	 RECIST 1.0  RECIST 1.1  Cheson 2007  Modified RECIST – specify:  Other criteria, Specify:

Efficacy Assessment Timepoints:	
Assessed during treatment at week 6 and week 12. Patients continuing treatment after week 12 will be assessed at 8 week intervals. Patients with progressive disease (PD), unacceptable toxicity, or who withdraw consent will be removed from the study.
 
Patients will be assessed at end of treatment visit
 
During follow-up, patients will be assessed every 3 months up to 6 months.
															
Efficacy Endpoints:	
  
 	Endpoint	Primary Analysis Population	Other Analysis Population	
   
 Primary	Overall Response Rate (ORR)	ITT Population		
 
 Secondary	Progression-Free Survival (PFS) Overall Survival (OS)	ITT Population		
  
					Endpoint	Primary Analysis Population	Other Analysis Population	Primary	Overall Response Rate (ORR)	ITT Population		Secondary	Progression-Free Survival (PFS) Overall Survival (OS)	ITT Population	
	Endpoint	Primary Analysis Population	Other Analysis Population													
Primary	Overall Response Rate (ORR)	ITT Population														
Secondary	Progression-Free Survival (PFS) Overall Survival (OS)	ITT Population														
Definition of Terms:																
 Response	
 Complete Response + Partial Response as best observed response
 
 Complete Response + Partial Response, confirmed with 4 weeks apart.
 
 Other criteria, specify:
															
 Clinical Benefit	
 Complete Response + Partial Response + Stable Disease as best observed response
 
 Complete Response + Partial Response (confirmed with      weeks apart) + Stable Disease (at least      weeks from start of treatment)
 
 Other criteria, specify:
															
 Progression	As defined in Appendix C of the protocol.															
 Subsequent Therapy																
 Treatment Failure																
Definition of Endpoints:	
Start Date:  Date of Randomization  Date of First Treatment
 
End Date (specify for all pertinent endpoints):
 
Overall Survival: Event = Death
 
  
 Situation	Date of Event or Censoring	Outcome	
   
 Death	Date of death	Event	
 
 Alive on date of data cutoff	Date last known alive	Censored	
 
 Alive before date of data cutoff, but status unknown on date of data cutoff (e.g. lost to follow-up)	Date last known alive	Censored	
  
				Situation	Date of Event or Censoring	Outcome	Death	Date of death	Event	Alive on date of data cutoff	Date last known alive	Censored	Alive before date of data cutoff, but status unknown on date of data cutoff (e.g. lost to follow-up)	Date last known alive	Censored
Situation	Date of Event or Censoring	Outcome														
Death	Date of death	Event														
Alive on date of data cutoff	Date last known alive	Censored														
Alive before date of data cutoff, but status unknown on date of data cutoff (e.g. lost to follow-up)	Date last known alive	Censored														

Progression-Free Survival: Event = Progression or Death			
	Situation	Date of Event or Censoring	Outcome
	No baseline assessment	Date of first treatment	Censored
	Progression documented between scheduled visits	First date of evaluated overall response = PD	Event
	No progression	Date of last evaluable tumor assessment	Censored
	Treatment discontinuation for adverse event or other reason	Date of last evaluable tumor assessment	Censored
	Death before first PD assessment	Date of death	Event
	Death before the next scheduled tumor assessment	Date of death	Event
	Death after one missed tumor assessment but before second missed tumor assessment	Date of death	Event
	Death after two or more missed tumor assessment	Date of last evaluable tumor assessment	Censored
 Overall Response Rate (ORR)	Default: Estimates of rates in each treatment arm		
 Disease Control Rate (DCR)	 Difference in rates & 95% confidence interval between treatment arms		
 Clinical Benefit Rate (CBR)	 p-value, specify statistical test:		
 Early Progression Rate (EPR)			
 Time To Progression (TTP)	Default: Estimates of medians in each treatment arm		
 Progression-Free Survival (PFS)	 Other quartiles or percentages of survival required, specify: probability evaluated at 6 month intervals		
 Overall Survival (OS)	 Hazard ratio & 95% confidence interval between treatment arms, unstratified		
 Duration of Response	 p-value, specify statistical test:		
 Duration of Stable Disease	 Hazard ratio & 95% confidence interval between treatment arms, stratified (specify stratification factor(s)):		
 Time To Treatment Failure (TTF)	 p-value, specify statistical test:		
 Other, Specify:			
7 Safety			
Adverse Events	Definition of Treatment-Emergent Adverse Event (TEAE): any adverse event (AE) that starts or worsens after the start of the first dose of study treatment up to 30 days post last dose.		
Laboratory Data	Data will be summarized by:  NCI-CTCAE for CTCAE-gradable parameters, and H/L for non-CTCAE-Gradable parameter		

H/L for all lab parameters

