7.3.7 Cycle 3 and Beyond, Day 1 (± 72 hours)

Regorafenib may not start until the patient's hematologic, liver and renal functions have been reconfirmed as eligible according to the Section 3.1 by the Investigator. Therefore, the regorafenib cycle starts on the day that treatment begins. If liver function toxicities are present, patient may be rechecked weekly for 2 additional weeks. Those patients with persistent liver function toxicities after this time will come off study, but will be followed until resolution.

- Physical examination, weight, and vital signs
- BP
- ECOG PS
- AE assessment
- Concomitant medication review
- CBC
- CMP
- PT/PTT/INR (for patients receiving Coumadin therapy)
- Biomarker blood sample collection (Day 30 (pre-dose) following SIR-Spheres treatment)
- CEA tumor marker

7.3.8 Cycle 3 and Beyond, Day 15

- PT/PTT/INR (for patients receiving Coumadin therapy)

7.4 Study Treatment Assessments – COHORT 2

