7.6 End-of-Treatment Visit

Patients are permitted to continue treatment with regorafenib until disease progression, or the patient is discontinued due to unacceptable toxicity or decision to discontinue treatment by the patient or the study physician.

If treatment is discontinued because of toxicity or any other reason(s) at a treatment visit and no study treatment is administered, that visit may fulfill the End-of-Treatment visit.

After withdrawal from or completion of protocol treatment, patients must be followed for any new AEs for 30 calendar days after the last dose of study drug.

The following end-of-treatment visit procedures will be performed.

- Physical examination, weight, and vital signs
- BP
- ECOG PS

CONFIDENTIAL

STUDY DEVICE: SIR-Spheres®

SCRI INNOVATIONS STUDY NUMBER: GI 189

DATE OF ORIGINAL PROTOCOL: 16 December 2013

Date of Amendment #1: 15 April 2014

Version 2.0

- AE assessment
- Concomitant medication review
- CBC
- CMP
- PT/PTT/INR (for patients receiving Coumadin therapy)
- Disease assessment
 - CT scan of chest, abdomen and pelvis
 - CEA tumor marker

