7.7 Follow-Up

7.7.1 Follow-up for Patients Who Discontinue Prior to Disease Progression

Patients discontinuing treatment for any reason other than PD will be monitored for evidence of disease progression. Patients will be followed every 3 months (± 1 month) for up to a maximum of 6 months after the last patient has been enrolled on study for disease progression. Assessments at these visits will be performed as described in Appendix A **Error! Reference source not found.** and Appendix B **Error! Reference source not found.**

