10.4.2 Efficacy Analysis

All efficacy analyses will be performed using the Intent-To-Treat Population.

- Overall Response Rate (ORR) is defined as the proportion of patients with observed CR or PR (i.e. 2 CRs or PRs at least 4 weeks apart) according to the RECIST 1.1 criteria.
- Progression Free Survival (PFS), defined as the time from the first day of study drug administration (Day 1) to disease progression as defined by the RECIST v1.1 criteria, or death on study. Patients who are alive and free from disease progression will be censored at the date of last adequate tumor assessment.
- Overall Survival (OS), defined as the time from the first day of study drug administration (Day 1) to death. Patients who are alive will be censored at the date of last known date alive.

For ORR, the estimates and the associated 95% confidence interval (based on the Clopper-Pearson method) in each treatment group will be calculated.

For PFS and OS, Kaplan-Meier curves will be generated and the median time to event and the associated 95% confidence interval will be provided.

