- j. CT scan of the chest, abdomen and pelvis will be obtained at baseline ≤ 28 days prior to the initiation of treatment. Assessments required the same day of SIR-Spheres administration can be obtained ≤ 7 days prior to SIR-Spheres treatment. Patients will be restaged on Week 6 and Week 12 after SIR-Spheres treatment according to RECIST v1.1. All assessments should be performed within 7 days of the schedule day of assessment. Patients with stable disease or better may continue treatment with regorafenib. CEA tumor markers must be assessed on Day 1 of each cycle and at the End of Treatment visit.
- k. Patients determined to have stable disease or better at the Week 12 restaging continuing treatment will begin 28-day treatment cycles (21 days oral regorafenib followed by one week rest). Patients will then be re-assessed according to RECIST v1.1 criteria every 8 weeks.
- l. All patients will undergo the End of Treatment visit assessments listed within 30 days after treatment ends due to completion of the planned study treatment period, or once a patient is discontinued due to unacceptable toxicity or decision to discontinue treatment by the patient or the study physician. If treatment is discontinued because of toxicity or any other reason(s) at a treatment visit and no study treatment is administered, that visit may fulfill the End of Treatment visit. After withdrawal from or completion of protocol treatment, patients must be followed for adverse events for 30 calendar days after the last dose of study drug.
- m. Patients will be followed every 3 months (± 1 month) for up to a maximum of 6 months after the last patient has enrolled on study for toxicity and disease progression.
- n. After disease progression is documented, patients will be followed every 3 months (± 1 month) for survival (e.g., date and cause of death) for up to a maximum of 6 months after the last patient has enrolled on study or death whichever comes first. Patients may be contacted during outpatient visits or by telephone.
- o. Patients will be assessed 7-4 days prior to SIR-Spheres treatment to determine the suitability for SIR-Spheres (see Section 7.2).
- p. Patients will self-administer regorafenib during Days 1-21.
- q. The Cycle 1 Day 22 physical examination, ECOG performance status, CBC, CMP, and PT/PTT/INR, tumor marker (CEA), adverse event evaluation, and concomitant medication review to be completed ≤ 7 days prior to SIR-Spheres radiation treatment.

STUDY DEVICE: SIR-Spheres®

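### The SAP's PFS table censors patients who stop treatment without excepting later progression or death, contrary to protocol 10.4.2 and to its own event rows

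*SAP*

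**What the plan says.** **SAP.** Section 5/6 defines the PFS event as progression or death and then lists situations with a date and an outcome. One row is "Treatment discontinuation for adverse event or other reason": censored, at the last evaluable tumor assessment. A separate row for patients without progression has the same date and outcome. Other rows make documented progression an event, and three rows make death an event. None of these is limited to patients still on treatment. The same section lists the end-of-treatment visit as an efficacy assessment and adds "During follow-up, patients will be assessed every 3 months up to 6 months".

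**Protocol.** Section 10.4.2 runs PFS from Day 1 "to disease progression as defined by the RECIST v1.1 criteria, or death on study". Its only censoring rule is "Patients who are alive and free from disease progression will be censored at the date of last adequate tumor assessment". Stopping treatment is not a reason for censoring. Section 7.7.1 states "Patients discontinuing treatment for any reason other than PD will be monitored for evidence of disease progression". Section 7.6 includes a "CT scan of chest, abdomen and pelvis" at the end-of-treatment visit, and footnote l of Appendix A says "All patients will undergo the End of Treatment visit assessments listed within 30 days after treatment ends".

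**The concern.** The SAP row and protocol 10.4.2 give different PFS outcomes for a patient who stops without progression and later progresses. The SAP does not acknowledge or justify the difference. Because the row overlaps the SAP's own event rows and nothing says which prevails, two programmers could code the same patient differently and both be following the plan.

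The row will be used. Protocol 3.3 lists toxicity, intercurrent illness and patient request among the reasons for stopping. For liver toxicity after SIR-Spheres, section 7.3.7 says "Those patients with persistent liver function toxicities after this time will come off study, but will be followed until resolution", and 7.4.4 has the same rule for Cohort 2. Under section 5.1, patients who fail the angiogram or lung-shunt scan are removed and replaced. In Cohort 1 that work-up falls in week 4, after regorafenib has started, so those patients are already in the ITT population. In Cohort 2 it precedes treatment, so they are not. The row can therefore act unequally on the two cohorts.

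Patients who stop for toxicity or decline may have a different prognosis from those who continue, in which case censoring them is informative.

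**Working it through.** The plan states no figure for this point, so the first check is of the rules.

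**1. One patient under each rule (illustrative).** Scan without progression on day 42, stop for an adverse event on day 50, progression documented on day 84, no evaluable scan between.
- Protocol 10.4.2, and the SAP event definition: event at 84 / 30.4375 = 2.76 months.
- SAP discontinuation row: censored. If the last evaluable assessment means the last one before the stop, the time is 42 / 30.4375 = 1.38 months.

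**2. Can the row be read harmlessly?** If it means patients who stopped and never had an event, it repeats the no-progression row exactly. It is then redundant. On any reading that makes it do something, it removes events. As worded, 'other reason' does not even exclude stopping for progression, which 3.3 lists.

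**3. How many events are at stake?** Simulation of 400,000 stoppers per scenario, all event-free at the stop.

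From the documents:
- End-of-treatment CT within 30 days of stopping (Appendices A and B, footnote l), then visits every 3 months (7.7.1), taken as 13 weeks.
- Cut-off 6 months after the last enrolment (10.5.1) in a 16-month study (synopsis). This leaves 16 − 6 = 10 months of accrual. Cohorts enroll one after the other, taken as 5 months each with even accrual, so follow-up is 11–16 months in Cohort 1 and 6–11 months in Cohort 2.
- Median PFS 1.9 months (Introduction, regorafenib arm of the cited phase III trial).

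Assumed: alternative median of 13 weeks; stop uniform over weeks 2–10; end-of-treatment CT uniform over 0–30 days; post-stop hazard multiplied by 1, 2 or 4.

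Share of stoppers whose event is seen by cut-off:

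| | Every event after the stop | Only events after the end-of-treatment CT |
|---|---|---|
| Cohort 1, hazard ×1 | 91–97% | 80–82% |
| Cohort 2, hazard ×1 | 70–84% | 60–68% |
| All scenarios | 70–100% | 53–82% |

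Events lost per cohort = 25 × stop rate × share. The low end uses the smallest share in the second column (52.7% before rounding) and so still counts progression on the end-of-treatment CT. The high end uses 100% and loses everything after the stop.

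| Assumed stop rate | Low | High |
|---|---|---|
| 10% | 2.5 × 0.527 = 1.3 | 2.5 × 1.00 = 2.5 |
| 20% | 5.0 × 0.527 = 2.6 | 5.0 × 1.00 = 5.0 |
| 30% | 7.5 × 0.527 = 4.0 | 7.5 × 1.00 = 7.5 |

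With the post-stop hazard unchanged, the range is 2.5 × 0.60 = 1.5 to 2.5 × 0.97 = 2.4 at 10% stopping, and 7.5 × 0.60 = 4.5 to 7.5 × 0.97 = 7.3 at 30%.

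**4. Does the median move?** Kaplan-Meier with exact event times, underlying median 1.9 months, 20% stopping at times independent of the event:

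| Post-stop hazard | Protocol 10.4.2 | SAP row, literal |
|---|---|---|
| ×0.5 | about 2.0 months | about 1.9 months |
| ×1 | about 1.9 | about 1.9 |
| ×2 | about 1.8 | about 1.9 |

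The literal row flatters PFS if stoppers do worse afterwards, understates it if they do better, and otherwise costs only events and precision.

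**The case against.** The strongest reply is that the literal reading may not be intended. The heading already fixes the event as progression or death. The table is not a clean partition: two of its death rows overlap harmlessly, and its only progression row speaks of progression between scheduled visits, so progression at a scheduled scan has no row at all. The censoring date is the last evaluable assessment, not the last before stopping, which fits a patient followed after the stop without progressing. This stands as evidence of loose drafting. It does not supply the missing qualifier, and the reading it supports leaves the row with no function.

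Other points stand as limits:
- Section 7.7.1 is a follow-up rule, not an endpoint definition. It shows that the data are collected; the conflict of definition is with 10.4.2.
- For deaths the conflict is less firm than for progression. The protocol counts only deaths on study and does not define the term, while section 7.5 takes patients with toxicity off the study.
- No bias in the median follows unless stopping is related to prognosis, which the documents do not quantify. Simulations that place the stop at a fraction of the patient's own event time show larger shifts, but they build that dependence in and are not relied on here.
- The SAP's follow-up line could mean 6 months per patient, which would lower the number of late events.
- PFS is secondary, with no test and no hazard ratio, and the OS table has no such row.

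**Conclusion.** The concern holds and should be fixed. Applied as written, the row gives the wrong PFS status under protocol 10.4.2 to a patient who stops treatment and later has RECIST progression, and it contradicts the table's own event rows. That conclusion is textual and needs no assumption.

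The size rests on assumed stop rates, stop times, hazards and accrual: about 1.3–2.5, 2.6–5.0 or 4.0–7.5 events per cohort of 25 at 10%, 20% or 30% stopping, and none if the row is read as covering only patients without a later event. The direction of any bias is not fixed. The effect falls on the event and censoring counts in SAP Table 6 and, where stopping is informative, on the medians, quartiles and 6-month-interval probabilities. No type I error is involved.

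**What to change.** - Delete the discontinuation row, or restrict it to patients with no later progression or death.
- State that the first RECIST progression or death is the event whether or not treatment has stopped, using the end-of-treatment and 7.7.1 scans. Censor patients who are alive and progression-free at the last adequate assessment, as in 10.4.2.
- State which row prevails when two apply.
- Define the protocol's term for deaths that count, and align with it the SAP row that censors deaths after two or more missed assessments. That rule, or censoring at discontinuation, can be kept as a sensitivity analysis.
- The sponsor should reconcile the passages that take patients with toxicity off the study (protocol 7.5, SAP assessment timepoints) with protocol 3.3, which speaks of study treatment, and 7.7.1, which continues follow-up. Withdrawal of consent stays as it is.

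The cost is SAP wording and one reconciliation of existing protocol text. No new visits or data are needed. The PFS estimates may move slightly in either direction.
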